## 10.6 Measures to Minimize Bias

### 10.6.1 Enrollment/Randomization/Masking Procedures

As randomization is done at the cluster (care team) level, this will only be performed at the beginning of the trial. The study statistician will perform the randomization utilizing SAS 9.4 stratified by agency. The PI will relay to the home care agencies which teams will serve as quality improvement program teams or control teams. The study RAs, study project director, and site-PIs will all be blinded to the assignment. Teams will be randomized in strata by agency and geographic location to ensure like care teams are assigned to each condition. Subjects will be assigned through usual practice to the care team that serves the geographic area they live in. We will sequentially recruit individuals as they are referred from agencies following the very clear, straightforward method described above in section [5.4](#).

Clinicians will be enrolled sequentially if they are eligible and all study personnel with the exception of the lead site PI and study statistician will be blinded as to the assignment of the clinicians within a performance improvement or usual care team.

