## **4 Study Design and Endpoints**

### **4.1 Description of Study Design**

This study will use a blinded cluster randomized controlled trial methodology. Each HHC care team will be randomized to either partake in the DSM-H performance improvement program or provide usual care. The project director based at NYU and RAs at all sites will be blinded to prevent bias in data collection. The study statistician based at NYU will perform the randomization utilizing SAS 9.4 stratified by agency and geographic location. The study PI will relay to the agencies which teams will serve as intervention or control. The study PI and statistician will not collect study data in order to maintain the integrity of the blinding. The potential for contamination between care teams randomized to receive the DSM-H performance improvement program and those who will provide usual care is minimal due to the nature of HHC clinician workflow where minimal time is spent in the office, and different care teams do not generally congregate with each other except during highly structured staff meetings. The investigators considered randomizing by site and using other HHC agencies; however, given the lack of contamination found in prior studies of the DSM-H combined with differences in care provision at other sites/locations and the need for a large number of clusters when using this methodology, the investigators felt this method was the most likely to provide valid and reliable results. It is not possible to randomize by patient in HHC because patients are seen by care teams in a given geographic region. Patients in the performance improvement group will receive care from a care team who has received the DSM-H performance improvement program, and those in the control will receive usual care from a care team who has not received the performance improvement program. Patients at the study sites are only cared for by members of the same care team and therefore there is no potential for patients to receive a mixture of care teams.

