## 10.4 Description of Statistical Methods

### 10.4.1 General Approach

Data Analysis will be performed using SAS 9.4. We will perform statistical tests to examine baseline differences between the quality improvement program and control groups. We will then perform unadjusted comparison of both primary outcomes (patient and caregiver quality of life, emergency room visits) and secondary outcomes (pain, BPSD, delirium, caregiver depression burden, and burnout, hospital and emergency room admissions) between groups. We will focus on the endpoint measure for quality of life, and 30 and 60-day outcomes for emergency room utilization. For primary and secondary outcomes, we will perform a time trend analysis using a mixed effects linear model (PROC MCM). Mixed effects regression is used to analyze longitudinal data with repeated measures accounting for intra-individual and group clustering. We intend to use multivariate mixed effects regression modeling as opposed to traditional linear modeling or ANOVA in order to control for unobservable confounding variables that are constant over time but differ across PWD and/or caregivers. For both primary and secondary outcomes, we will then repeat the above analyses adjusting for baseline variables as covariates for a more efficient measurement of the effects of the quality improvement program. We will also perform correlation analyses to explore the relationship between pain and BPSD, and PWD and caregiver QOL through plotting scores over time and then if a significant correlation is present through adding to our mixed effect model. For utilization data, we will perform logistic regression to examine whether the patient is more or less likely to have a hospitalization or ER visit compared when receiving the quality improvement program at 30 and 60 days. We will then perform a Poisson Count Regression to compare the total number of hospitalizations and ER visits at each timepoint. In these models we will utilize a random effect to measure for clustering.

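### Teams are randomised within agency and geographic strata, but no specified model contains agency or stratum, so standard errors will be too large if agency is prognostic

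*Combined protocol and SAP*

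**What the plan says.** **Randomisation.** Section 4.1 states: "The study statistician based at NYU will perform the randomization utilizing SAS 9.4 stratified by agency and geographic location". Section 10.6.1 describes the strata twice. One sentence names agency alone: "The study statistician will perform the randomization utilizing SAS 9.4 stratified by agency". A later one names both factors: "Teams will be randomized in strata by agency and geographic location to ensure like care teams are assigned to each condition". The number of geographic strata is not given. The Protocol Summary allots 12 teams to VNAHG, 5 to Utah and 3 to Miami.

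**Analysis.** Section 10.4.1 describes the mixed model as "accounting for intra-individual and group clustering". For the logistic and Poisson utilisation models it says: "In these models we will utilize a random effect to measure for clustering". The Protocol Summary gives the same picture. None of these places names agency, geography or stratum as a model term, and the grouping unit is not defined.

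**Adjusted repeat.** Section 10.4.1 adds: "we will then repeat the above analyses adjusting for baseline variables as covariates for a more efficient measurement". The covariates are not listed. The baseline comparison in section 10.4.4 lists demographic, literacy, functional and comorbidity variables; neither agency nor geography is among them. Section 10.1 rules out a formal SAP, so no separate analysis document is promised that would supply the terms.

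**The concern.** Stratified randomisation spreads each agency's teams across both arms, so agency differences largely cancel from the treatment contrast. A model without agency leaves those differences in the between-team variance from which the standard error is built. The estimate is then more precise than the model reports: intervals are too wide, the test falls below its nominal level, and power may be lost.

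Two features of this trial make the point worth settling. There are only 20 teams, so the between-team component carries much of the variance. And agencies with 5 and 3 teams cannot be split evenly, so some imbalance by agency remains, which only an agency term removes.

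With no SAP and no named covariates, whether agency enters could also be decided after the results are known.

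**Working it through.** **Inputs.** From section 10.5: effect δ = .45 SD, ICC ρ = .05, 15 dyads per team, 20 teams (10 per arm), alpha .05 (taken as two-sided), power .80. From the Protocol Summary: 12, 5 and 3 teams per agency. Assumed, because the documents do not give it: the share *s* of between-team variance among the trial's teams that agency explains.

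**1. The plan's own figure, no stratum term.**
- Variance of a team mean, in SD² units: ρ + (1 − ρ)/15 = .05 + .06333 = .11333.
- Variance of the arm difference: .11333 × (1/10 + 1/10) = .02267, so SE = .1506.
- Noncentrality: .45/.1506 = 2.989. Noncentral t with 20 − 2 = 18 df gives power **.807**.

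This reproduces the stated .80 without any covariate. If the plan's 15% of variance explained by covariates is applied at team level, power is .833.

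**2. With agency as a fixed effect.** An agency with *a* teams in one arm and *b* in the other contributes ab/(a + b) to the information. With splits of 6/6, 3/2 and 2/1:
- 36/12 + 6/5 + 2/3 = 3 + 1.2 + .667 = 4.867.
- The multiplier is 1/4.867 = .2055, in place of .20.
- Variance = (.05(1 − s) + .06333) × .2055, with 20 − 1 − 3 = 16 df.

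| Share s (assumed) | Team-mean variance | SE | .45/SE | Power with agency | Power without |
|---|---|---|---|---|---|
| 0% | .11333 | .1526 | 2.949 | .791 | .807 |
| 10% | .10833 | .1492 | 3.016 | .808 | .807 |
| 25% | .10083 | .1439 | 3.126 | .835 | .807 |
| 50% | .08833 | .1347 | 3.340 | .880 | .807 |

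The largest loss is .807 − .791 = .016. Break-even is near 10%. The gains are .835 − .807 = .028 and .880 − .807 = .073. Simulated trials with the same 12/5/3 structure agree: with agency .793, .811, .835 and .880; without it .809, .809, .810 and .814.

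**3. Level of the test without agency.** In simulation under no effect, type I error without agency was 3.8% to 4.3% at s = 25% and 3.1% to 3.4% at s = 50%, depending on how the agency effects were set. With agency in the model it stayed between about 4.4% and 5.2%. The cause is visible at s = 50%: without agency the reported SE averaged about .150, while the estimate itself varied with an SD of about .140 to .142.

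**4. Finer strata.** The number of agency-by-geography strata is not stated. With eight (an assumption), df = 20 − 1 − 8 = 11. Keeping the even multiplier of .20, power is .777, .795, .822 and .868 at 0%, 10%, 25% and 50%. Break-even then lies between 10% and 25%.

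**The case against.** The strongest reply is that nothing the plan claims actually fails. The 80% power holds without stratum terms, and the omission makes the test conservative, so it cannot manufacture a positive result. Agency is unspecified in the adjusted repeat rather than excluded from it. All of this stands. What remains is that the plan, followed as written, does not analyse by the groups it randomised within.

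Several stronger readings are tempting and should be resisted:

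- **That the models handle team clustering and nothing else.** The mixed model also handles repeated measures within person, and the grouping unit is left undefined.
- **That section 4.1 shows the three agencies differ.** Its remark on differences in care provision explains why randomising by site with other agencies was rejected. It does not compare the trial's own agencies, and it says nothing about outcome variance.
- **That stratification was intended to gain precision.** The aim stated in section 10.6.1 is comparability of teams.
- **That an agency term certainly raises power, or costs under one point.** The gain depends on a share the documents do not give. With even splits the formula gives .801 at 0%, but 5 and 3 teams cannot split evenly; the realistic figure is .791, slightly below the planned .80.
- **That every geographic stratum should enter.** With fine strata the lost degrees of freedom can outweigh the gain.

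**Conclusion.** The point holds as an omission whose cost is conditional. The strata used in the randomisation appear in no specified model. If agency is prognostic, standard errors will be too large and the test will run at roughly 4% or 3% instead of 5%, for assumed shares of 25% or 50%. A reader might infer that the trial is underpowered or exposed to false positives; the documents support neither.

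Adding agency costs about 1.6 points of power at worst, breaks even near 10% of between-team variance explained, and gains about 2.8 points at 25% and 7.3 at 50%. These figures rest on the plan's ICC and team sizes, equal team sizes, a two-sided test with between-team degrees of freedom, and the assumed shares. They cover only the continuous quality-of-life outcome. The logistic and Poisson models for emergency visits and admissions were not computed.

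**What to change.** In section 10.4.1:

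- Define the group random effect as the care team.
- Enter agency (3 levels) as a fixed effect in the primary and secondary mixed, logistic and Poisson models, both with and without the baseline covariates.

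In section 10.6.1:

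- Reconcile the sentence naming agency alone with the one naming agency and geographic location, and state how many strata were used.
- Add geographic strata to the models only where they are few enough to be estimated. If sparse strata are to be collapsed, exempt agency from that rule: the agency with 3 teams can never have two per arm and would otherwise lose its own level.

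The cost is a few sentences and two degrees of freedom for agency (18 to 16), which is at most about 1.6 points of power for the quality-of-life outcome. No change to the sample size is needed.

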### 10.6.2 Evaluation of Success of Blinding

Not applicable

### 10.6.3 Breaking the Study Blind/Participant Code

Intentional breaking of the blind will only be performed in case of SAE, and then only to the site PI, but not the site RA or project director.

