### 8.2.2 **Relationship to Study Quality Improvement Program**

CONFIDENTIAL

This material is the property of the NYU School of Medicine and Langone Medical Center. Do not disclose or use except as authorized in writing by the study sponsor  
 Interventional Template Version: 28 APR 2017

The PI or site PI will assess the AE's relationship to study quality improvement program, and will be part of the documentation process, but it is not a factor in determining what is or is not reported in the study. If there is any doubt as to whether a clinical observation is an AE, the event should be reported. All AEs must have their relationship to study agent assessed. In a clinical trial, the study product must always be suspect. To help assess, the following guidelines are used.

- **Related** – The AE is known to occur with the study agent, there is a reasonable possibility that the study agent caused the AE, or there is a temporal relationship between the study agent and event. Reasonable possibility means that there is evidence to suggest a causal relationship between the study agent and the AE.
- **Not Related** – There is not a reasonable possibility that the administration of the study agent caused the event, there is no temporal relationship between the study agent and event onset, or an alternate etiology has been established.

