## 10.5 Sample Size

Power analyses were conducted using Optimal Design software. Given that this study is randomized at the cluster level, we must control for intra-class correlation, and have therefore calculated all power with an intra-class coefficient of .05, which is more conservative than the most recent clustered palliative care study and aligns well with prior community-based cluster trials. The Quality of Life in Alzheimer's Disease as the primary outcome measure in aim 1 has an average score of 33.1, standard deviation of 5.9. A .5 standard deviation difference in this measure would be clinically meaningful. Therefore, in a 2-sample comparison with a power of .80, an alpha of .05 and covariates that account for a cumulative 15% of the variance in outcome would require 15 dyads per cluster, and 20 clusters (10 per arm) at 60 days to detect a medium effect ( $\delta = .45$ ). For mixed effects linear models, the projected sample size will also allow us to detect a medium linear treatment effect ( $\delta = .45$ ) between groups in unadjusted analyses (assuming 15 dyads per cluster, 20 clusters, 4 observations, and an ICC = .05). Although there are no closed-form equations for calculating the power of linear models that include covariates, any non-zero correlation between covariates and the outcome will reduce the unexplained (error) variance thus increasing the statistical power of our tests, and reducing the minimum detectable effect size. As such, the detectable effect size estimated for the unadjusted analyses can be considered an upper bound estimate for the effect size detectable in adjusted analyses. **We will recruit until we have reached 15 completed cases in each cluster (N=300).** Conservatively anticipating a 15% dropout over the 60 days requires a **total recruitment goal of 345 dyads**. As almost 20,000 patients are seen each year in the three HHC agencies in this study, approximately 30% with ADRD, we do not expect any difficulty recruiting this sample, even with an unanticipatedly high rate of dyads declining to participate.

In addition, for fidelity monitoring, as discussed in section [6.1.6.1](#), we will consent **300 clinicians** at the participating HHC agencies on usual care and quality improvement care teams to complete fidelity monitor by performing the DSKA survey. These clinicians are not study subjects but will be consented as they are

CONFIDENTIAL

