### **14 Data Handling and Record Keeping**

#### **14.1 Data Collection and Management Responsibilities**

All data including the consent forms will be collected and maintained electronically in NYULMC RedCap or on an MCIT-managed network drive. Referral submissions sent via encrypted transfer or secure email will be uploaded directly into redcap, the study log, by the research coordinator or project director.

Enrolled subjects who request to receive an email or text message to reminder them of upcoming study visits, will receive a notification through REDCap. Email notifications will be performed using REDCap survey function. SMS (text) messages will be completed through a linked REDCap and Twilio account. When a subject requests to receive a text message to their cell phone, REDCap requests that action through Twilio. When the subject responds to the message, Twilio relays the information back to REDCap. The data from this exchange is stored in the REDCap database. Twilio does not store any data nor does it keep a log of its actions. Further, REDCap goes to great length to ensure that SMS transcriptions do not stay in Twilio's logs but are removed shortly after being completed. This is done for security and privacy concerns (e.g., HIPPA), in which the subject's phone number and response to confirm the visit are not permanently logged on Twilio's servers but instead remain securely in REDCap.

Data collection is the responsibility of the clinical trial staff at the site under the supervision of the site PI. The investigator is responsible for ensuring the accuracy, completeness, legibility, and timeliness of the data reported.

All source documents should be completed in a neat, legible manner to ensure accurate interpretation of data. Black ink is required to ensure clarity of reproduced copies. When making changes or corrections, cross out the original entry with a single line, and initial and date the change. DO NOT ERASE, OVERWRITE, OR USE CORRECTION FLUID OR TAPE ON THE ORIGINAL.

Copies of the electronic CRF (eCRF) will be provided for use as source documents and maintained for recording data for each participant enrolled in the study. Data reported in the eCRF derived from source documents should be consistent with the source documents or the discrepancies should be explained and captured in a progress note and maintained in the participant's official electronic study record.

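### Breaking the blind to a site PI for one SAE reveals the whole care team's arm, which undercuts the site-PI blinding in 10.6.1

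*Combined protocol and SAP*

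**What the plan says.** Section 10.6.1 sets the allocation and the masking. On allocation: "As randomization is done at the cluster (care team) level, this will only be performed at the beginning of the trial". On masking: "The study RAs, study project director, and site-PIs will all be blinded to the assignment". Section 4.1 ties each patient to one team: "Patients at the study sites are only cared for by members of the same care team". It names the project director and the research assistants as blinded but does not mention site PIs.

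Section 10.6.3 then provides: "Intentional breaking of the blind will only be performed in case of SAE, and then only to the site PI". It excludes the site research assistant and the project director from the disclosure. It does not say which SAEs qualify, who decides, whether the break is recorded, or what the site PI may do afterwards.

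The site PI's duties are set out elsewhere. Section 8.2.2: "The PI or site PI will assess the AE's relationship to study quality improvement program". Section 8.2.3 gives the site PI or PI the judgement of expectedness, and 8.6 has all site PIs take part in classifying AEs, SAEs and unanticipated problems. Section 14.1: "Data collection is the responsibility of the clinical trial staff at the site under the supervision of the site PI". Section 5.4 has the PI and site PI train the staff who assess capacity and obtain consent.

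**The concern.** The rule in 10.6.3 would suit an individually randomized trial, where a break discloses one participant's assignment. Here there is no participant-level assignment to disclose. Telling a site PI the arm of one patient tells that person the arm of the team, and so of every dyad the team has contributed or will contribute.

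Two things are at stake. First, relatedness judgements by a site PI become arm-aware for that team, and relatedness has consequences. Sections 8.4 and 8.5 tie expedited submission of SAEs to their being study-related, and 8.7 halts the study for SAEs caused by the program. Second, dyads are recruited after teams are randomized and outcomes come from interviews. A supervisor of recruiters and interviewers who knows the arms is a recognised risk in that setting.

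The plan states no need that the break would meet. The SAE steps in 8.1, 8.1.1 and 8.4 are to notify the subject's health care provider, the IRB and the DSMB, and none depends on the arm.

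**Working it through.** The plan gives no expected number of SAEs or of unblindings, so there is no stated figure to reproduce. The check has three steps.

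**1. What one break reveals.** Teams are randomized once (10.6.1) and a patient is seen by one team only (4.1). Patient's arm = team's arm. The sample size section plans 15 completed dyads per team: "would require 15 dyads per cluster, and 20 clusters (10 per arm) at 60 days". Its enrolment target is a "total recruitment goal of 345 dyads", so 345 / 20 = 17.25 enrolled dyads per team on average. One break therefore discloses the arm of about 15 to 17 dyads.

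**2. How many teams could be newly revealed.** The Protocol Summary gives 12 clusters at VNAHG, 5 at Utah and 3 at Miami. Section 15.4 lists the PI and two local site PIs. VNAHG falls under the lead site, and the lead PI relays the allocation to the agencies (4.1, 10.6.1), so 10.6.3 discloses nothing new there. Assuming that the two local site PIs are at Utah and Miami, the ceiling is 5 + 3 = 8 of 20 teams (40%), split between two people.

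**3. How often a team has an SAE that would permit a break.** Section 8.1 includes hospitalization of either dyad member among the monitored serious events, and the general definition in 8.1.1 includes a hospital stay. The documents give no per-dyad SAE risk, so the risk p is an assumption shown over a range. Treating dyads as independent, P(team has at least one) = 1 − (1 − p)^n.

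| Assumed p | n = 15 | Expected teams of 8 (n = 15) |
|---|---|---|
| 5% | 1 − 0.95^15 = 0.537 | 4.3 |
| 10% | 1 − 0.90^15 = 0.794 | 6.4 |
| 25% | 1 − 0.75^15 = 0.987 | 7.9 |

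Counting enrolled dyads (n = 17.25) instead of completed ones gives 0.587 at 5% and 0.838 at 10%, or 4.7 and 6.7 of 8 teams. Half of the teams have at least one SAE once p reaches 1 − 0.5^(1/15) = 4.5%, or 1 − 0.5^(1/17.25) = 3.9% on enrolled dyads.

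These are chances that an SAE occurs. For a given p and n they equal the chance of unblinding only if the blind is broken at every SAE, so they are upper bounds on it.

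**The case against.** The strongest reply is that 10.6.3 is a limit and not a trigger. It says when a break may happen and does not say that every SAE leads to one. A reader might infer that site PIs will soon know most teams' arms, and the documents do not support that. It would need a break at every or most SAEs. Trial-wide, local site PIs can learn at most 8 of 20 teams on the reading of 15.4 above. Nor need it be soon. At 345 / 39 / 20 = 0.442 dyads per team per month, 24% of teams would have had an SAE by month 12 of accrual at p = 5%, and 43% at p = 10%.

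A reader might also take the admission figures in 4.2.1 as showing that exposure is certain. Those figures imply 63.8 / 0.10 = 638 admissions per 1000 patients. That is a count of events over a period the section does not state. Turning it into 47% of patients with an admission needs a Poisson assumption (1 − exp(−0.638) = 0.472) that the plan does not make. The scope of SAEs is also unsettled: the trial-specific list that closes 8.1.1 names only caregiver suicide attempt and the two kinds of death, and on that list exposure could be much lower.

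Third, the site PI rates no outcome, and 10.6.3 keeps the research assistants and project director blinded. That stands: direct outcome rating is protected, and no direct route to a primary endpoint is shown.

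Fourth, 10.6.3 can be read as a stated exception to 10.6.1, and causation by a team-level program does depend on whether the team had the program. This is fair as far as it goes. It is a reason for some arm-aware review, which the lead PI can already give, and the DSMB already receives unblinded interim results (10.4.2). It is not a reason to unblind the site PI. Sections 8.2.2 and 8.8.2 also point to wider reporting whatever the relatedness, which softens the reporting consequence but leaves the halting rule in 8.7 resting on causation.

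**Conclusion.** The point holds in a limited form. Under cluster allocation, each break permitted by 10.6.3 is a team-level break, made to a person whom 10.6.1 requires to be blinded and who helps classify SAEs and supervises data collection. The rule has no criteria, decision-maker or log, and the plan gives no step that needs it.

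The size is bounded and uncertain. At most 8 of 20 teams are newly exposed if the local site PIs are at Utah and Miami. If hospitalization counts as an SAE and p is 5% or more, most of those teams will have at least one event that permits a break. How many breaks follow cannot be derived from the text. The calculation rests on the assumed p, independence of dyads, and a break at every SAE as the limiting case.

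The exposure is in relatedness and expectedness judgements and in supervision of recruitment and data collection. It would be wrong to conclude that outcome assessors are unblinded or that the efficacy comparison is shown to be biased.

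**What to change.** Change 10.6.3 so that an SAE does not by itself unblind the site PI. The site PI classifies events without knowing the arm, and any review that needs the arm is done by the lead PI, who already knows it, and by the DSMB. State that any exceptional break reveals the whole team's allocation, say who may authorise it and on what grounds, and log it with the date and the team.

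Reconcile 4.1, 10.6.1 and 10.6.3 on whether site PIs are blinded. In the same edit, settle whether the SAE list in 8.1 or the narrower one closing 8.1.1 applies, since that decides how often the question arises. Also check the monthly champion calls with the investigators in 6.1.6, which could reveal allocation to a site PI by another route that this change would not close.

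The cost is protocol wording and slightly more SAE review for the lead PI. The lead PI's own judgements remain arm-aware, as they are now.
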